10.2 Safety Evaluations

10.2.1 *Brief Physical Examination*

A brief physical exam will be performed at Visit 1/Screening and Visit 6/EOT. The exam will include examination of head and neck, dermatological, cardiovascular, respiratory, gastrointestinal (abdomen), and gross motor and gait. Abnormalities at Visit 1/Screening will be recorded as medical history. Any new or worsening abnormalities at Visit 6/EOT (and subsequent visits, if applicable) will be recorded as AEs. Directed physical exams will be performed at subsequent follow-up visits until the finding has resolved or stabilized in the opinion of the investigator.

10.2.2 *Vital Signs*

Vital signs including temperature, systolic and diastolic blood pressure, heart rate, and respiration rate will be measured at Visit 1/Screening, Visit 2/Baseline, and Visit 6/EOT. Assessments will also be performed at any subsequent follow-up visits if the results from the preceding visit are materially abnormal and clinically significant in the opinion of the investigator. Assessments will be made after the subject has rested in a seated position for at least five minutes. Height and weight will only be measured at Visit 1/Screening.

10.2.3 *Local Skin Reactions*

LSRs (burning/stinging, edema, and folliculitis) will be assessed for each Target Plaque at every visit (except Screening) using a 4-point ordinal scale (0=none, 1=mild, 2=moderate, 3=severe). Only LSRs that require medical intervention (e.g., prescription medication) will be documented as AEs. Any LSRs that are not listed above will be recorded as AEs.

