6.3 Warnings, Precautions, and Contraindications

These test articles are for topical use only. Care should be taken to avoid contact with eyes and all mucous membranes. If contact with eyes occurs, rinse thoroughly with water.

Subjects with a known sensitivity to any of the ingredients in the test articles should not participate in this study.

Should skin irritation or rash develop, discontinue use and contact the investigator.

In case of accidental ingestion, subjects should contact the investigator immediately.

Keep test articles out of reach of children/pets.

The effects of the test article in nursing mothers, pregnant women, and their unborn children are unknown. WOCBP must not be pregnant or planning a pregnancy during the study period.

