13. END OF STUDY CRITERIA

At the end of each subject's participation in the study, the investigator will complete an End of Study Disposition form for all completed and discontinued subjects.

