13.1 Completion of the Study

Subjects who complete the four-week course of treatment as specified in this protocol and return for Visit 9/EOS will be considered to have completed the study.

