13.2 Subject Discontinuation

A subject may be withdrawn from the study prior to completion for any of the following reasons:

- AEs
- Death
- Lack of efficacy (defined as the lack of expected or desired effect related to a therapy)
- Lost to follow-up
- Non-compliance with study drug
- Physician decision
- Pregnancy
- Progressive disease (defined as a disease process that is increasing in extent or severity)
- Protocol deviation
- Study terminated by Sponsor

- Withdrawal by subject; NOTE: if the subject decides to withdraw from the study due to an AE then it should be classified as withdrawal due to an AE
- Other (e.g., any reason that may affect the outcome of the study or safety of subjects)

If a subject withdraws from the study prematurely for any reason, the site should make every effort to have the subject return to the clinic to perform all of the required visit activities for Visit 6 if the subject is withdrawing during the treatment phase of the study or Visit 9 if the subject is in the post-treatment follow-up phase of the study and to collect and reconcile all test articles (if applicable). If the subject will not return to the clinic, the site should make every attempt to contact the subject; otherwise the subject will be considered lost to follow-up.

When a subject is withdrawn from the study for a test article related AE (as defined in [Section 14.2](#)), when possible, the subject should be followed until resolution or stabilization of the AE. If the subject is discontinued from the study due to pregnancy, the pregnancy and its outcome should be followed.

Subjects who are prematurely withdrawn or discontinued from the study will be replaced until approximately 20 subjects have completed the study.

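### A listed local skin reaction that makes a subject stop a test article without treatment need not be recorded as an AE

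*Combined protocol and SAP*

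**What the plan says.** Section 10.2.3 has burning/stinging, edema and folliculitis graded 0 to 3 on each Target Plaque at every visit after Screening. It then gives two rules on AE status. For the three listed reactions: "Only LSRs that require medical intervention (e.g., prescription medication) will be documented as AEs". For all others: "Any LSRs that are not listed above will be recorded as AEs". The Local Skin Reactions paragraph of the synopsis repeats both.

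Section 6.3 instructs subjects: "Should skin irritation or rash develop, discontinue use and contact the investigator".

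On leaving the study, Section 13 says "the investigator will complete an End of Study Disposition form for all completed and discontinued subjects". Section 13.2 introduces its list of reasons with "A subject may be withdrawn from the study prior to completion for any of the following reasons". AEs are one listed reason; physician decision, withdrawal by subject and other are separate ones. A note attached to withdrawal by subject adds "if the subject decides to withdraw from the study due to an AE then it should be classified as withdrawal due to an AE". For withdrawals caused by a test-article-related AE, Section 13.2 asks that "when possible, the subject should be followed until resolution or stabilization of the AE". Section 14.2 asks for suitable follow-up of subjects whose AEs cause them to interrupt or stop test article.

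Section 17.4.2 plans LSR frequencies by treatment, an AE listing (course, severity, relationship, outcome) and AE tables by treatment. Section 17.4.1.1 plans treatment duration, number of applications and percent of expected doses by treatment.

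**The concern.** The protocol tells subjects to stop for skin irritation, but its AE rule for the listed reactions looks only at whether treatment was needed. A subject with marked burning who obeys Section 6.3, stops, and recovers without medication does not meet the only stated trigger. Where later provisions attach consequences to such a stop, they attach them to an AE.

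Tolerability is part of the primary objective in Section 3. Each plaque receives one product, so a reaction that makes a subject stop one vial can be attributed to DUR-928 or to vehicle, provided the cause and the plaque are on record. If they are not, a relevant tolerability signal in a study of about 20 subjects can be missing from the AE counts. Withdrawn subjects are also replaced (Sections 5.1.3 and 13.2), and the per-protocol population requires completion (Section 17.2.3).

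**Working it through.** The protocol gives no figure to reproduce, since Section 17.1 reports no sample size calculation. The check is a comparison of sections.

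1. **AE status.** The general definition in Section 14.1 is broad enough to cover any of these reactions. Section 10.2.3 is specific and restrictive, and it narrows that definition for the three listed LSRs. No other visible section makes a stop or an interruption a trigger.

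2. **The route to an untreated stop.** Section 6.3 names irritation and rash. Rash is not a listed LSR, so it is always an AE. Irritation felt as burning/stinging is a listed LSR. The subject stops and contacts the investigator, and nothing in that sequence requires treatment.

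3. **What depends on AE status.** Three provisions do: follow-up in Section 14.2 after a stop or interruption; follow-up in Section 13.2 after withdrawal for a related AE; and the note in Section 13.2 that moves a subject's own decision into the AE category. If the reaction is not an AE, none applies as written, and the exit may be filed under a non-AE reason.

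4. **What is recorded anyway.**
   - LSRs present at a visit are scored per plaque through Visit 9 (Day 57), whether or not they are AEs.
   - A subject withdrawing during treatment should return for the Visit 6 activities, which include LSR scoring and a physical examination with a dermatological component. Under Section 10.2.1, new or worsening findings at that examination become AEs and are followed to resolution or stability.
   - The Disposition form covers everyone. Section 13.1 defines completers as "Subjects who complete the four-week course of treatment as specified in this protocol and return for Visit 9/EOS", so a permanent stop fails that definition and the form may prompt a reason.

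5. **What can still be missed.** Treatment-period visits fall nominally on Days 1, 8, 15, 22 and 29, which is 7 days apart. The visible text gives no recall period for LSR scoring. A reaction that starts after one visit, leads to a stop and clears before the next could score 0. Burning/stinging is a symptom, so the Visit 6 examination may not find it. For an interruption, or a stop by a subject who stays in the study, no visible text requires a reason; the Section 13.2 list concerns withdrawal from the study.

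6. **What the planned outputs show.** LSR frequencies are not linked to stopping. The AE listing does not name action taken with test article. The compliance summary shows missed doses by treatment but not why. For example, assume 28 expected doses (once daily for four weeks) and take the synopsis threshold of 70%. Then 0.70 × 28 = 19.6. Missing 8 doses leaves 20/28 = 71.4%, above the threshold; missing 9 leaves 19/28 = 67.9%, below it. A reaction that costs nine doses would appear as low compliance, with no planned output giving tolerability as the reason.

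7. **Scale.** One such subject is 1/20 = 5% of planned enrolment, or 1/15 = 6.7% of the planned evaluable subjects. How many would be affected cannot be derived from the documents.

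**The case against.** The rule is a deliberate convention. Section 10.1.5 treats pruritus the same way, as an AE only if therapy is needed. Reactions scored on their own scale are kept out of AE counts unless treated, which avoids counting them twice. Much is captured regardless: per-plaque scores to Day 57, the Visit 6 dermatological examination, diary dates and times, accountability at each treatment visit, and dose counts by treatment. Section 6.3 also has the subject contact the investigator, so the site knows of the stop. An investigator might regard an ordered stop as medical intervention. The eCRF and Disposition form fields are not shown, and an action-taken field may exist.

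Most of this stands, and it limits the point. Two parts do not close the gap. A stop begun by the subject under Section 6.3 fits poorly with medical intervention when the example given is prescription medication. And an action-taken field would not by itself change the AE rule or add a summary. The pruritus convention is no argument against a stop trigger: leading to a stop is a different and stronger signal than being present at a visit.

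A reader might infer that these reactions go unrecorded, or that stops leave no trace. The documents do not support that. What can be lost is AE status, the follow-up and coding tied to it, and the link between the reaction and the stop.

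**Conclusion.** The point holds in a narrow form and is minor. Read as written, Section 10.2.3 and the synopsis allow a listed LSR that leads to interruption or discontinuation without treatment to stay out of the AE counts, and to miss the AE-tied provisions of Sections 13.2 and 14.2. This mainly concerns burning/stinging and reactions that resolve before the next visit. Edema or folliculitis still visible at Visit 6 may be picked up through Section 10.2.1, although the restrictive wording of Section 10.2.3 could be read as overriding that route.

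The conclusion assumes that sites apply the medical-intervention rule literally and that nothing in the unseen forms or redacted appendices adds a stop trigger. No frequency is claimed, and the text does not show that tolerability will be under-reported, only that it can be.

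**What to change.** In Section 10.2.3 and the matching synopsis paragraph, document a listed LSR as an AE if it requires medical intervention or leads to interruption or discontinuation of either test article, and record the Target Plaque. In Section 17.4.2, add a count by treatment of LSRs and AEs that led to interruption or discontinuation of test article. The stopping instruction in Section 6.3 needs no change.

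The cost is at most one eCRF field (action taken with test article, by plaque, if not already there), one small table and slightly higher AE counts.

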11. PHOTOGRAPHY

Photography documentation is required in this study. Photographs taken as part of this study will be used to document the effects of treatment, AEs, or other findings during the study. All subjects will be asked to consent to the collection of photographs of their Target Plaques. Digital photographic records of the two Target Plaques (A & B) will be generated for each plaque site before the first application of test article and at each subsequent visit. To help with treatment identification, each Target Plaque site will be marked by a specific label on the photographs taken. Photographs of test sites will be taken under identical conditions, as much as possible, to enable proper comparisons to be made as detailed in the Study Photo Guide. Photographs shall be used as supportive documentation of efficacy and safety outcomes for this study but are not to be used by the investigator for grading or for any other assessment. An independent photo review may be performed at the discretion of the Sponsor. Any photographs taken of readily identifiable features (e.g., the face) will be de-identified (i.e., a masking bar over the eyes). In addition, photographs may be taken at the discretion of the investigator at any time to document the subject's progress in the study, AEs, or other findings of note.

Note: Subjects who decline to have photographs taken during the conduct of study may not participate in the study given that photography is required. If a subject initially consents to photographs, then declines further photography, the Sponsor may use the photographs taken under consent for the purposes noted above.

Subjects will also be instructed to take daily photographs of the treatment area during the occlusion step. At each visit, the daily photographs will be reviewed by the study staff to support compliance only. Daily photographs will not be collected or used as supportive documentation of efficacy or safety outcomes for this study.

12. LABORATORY TESTS

12.1 Blood Chemistries, Hematology, and Urinalysis

[figure not shown]
Urine and blood samples will be collected from each subject for safety laboratory analysis at Visit 1/Screening and Visit 6/EOT; clinical laboratory tests will also be performed at any subsequent follow-up visits if the results from the preceding visit are materially abnormal and clinically significant in the opinion of the investigator. Subjects must be fasting (approximately 8 hours) for Visit 1/Screening and, if possible, for Visit 6/EOT (and subsequent visits, if applicable); however, if a subject arrives at the clinic for Visit 6/EOT (or subsequent visits, if applicable) without fasting for at least eight hours, laboratory specimens may be collected as non-fasting, at the discretion of the investigator, and with the appropriate fasting status documented on the lab requisition form. Any new or worsening clinically significant abnormalities at Visit 6/EOT (and subsequent visits, if applicable) will be recorded as AEs. At the discretion of the investigator, clinical laboratory tests can be conducted at additional visits.

Product Name: DUR-928 Topical Solution
Sponsor Name: Therapeutics, Inc.

Protocol: C928-015
Protocol Date: May 22, 2019, v4.0

The following laboratory tests will be performed:

CCI

Sample collection, handling, labeling, and shipping should be done following the instructions provided by the relevant certified laboratory and the applicable local regulations.

The investigator must review all the subject's laboratory reports in a timely manner. **NOTE:** The investigator will initial and date each laboratory report to indicate his/her review. The investigator will note, directly on the laboratory report, whether or not any abnormal test results are clinically significant or not clinically significant. Clinical significant laboratory abnormalities that are present at Screening and/or Baseline must be documented in the subject's medical history. In addition, the investigator must complete an appropriate AE form for any new or worsening abnormal test results that are identified as clinically significant after Baseline.

AEs that may be associated with venipuncture and that must be included in the informed consent include:

- Pain
- Bruising
- Bleeding at the puncture site
- Fainting
- Inflammation of the vein

12.2 Urine Pregnancy Tests

A UPT will be performed at Visit 1/Screening, Visit 2/Baseline, and Visit 6/EOT for WOCBP.

The UPTs will be performed at the study site, if the site is registered and conforms to Clinical Laboratory Improvement Amendments (CLIA) regulations for such testing (possesses a current valid CLIA Certificate of Waiver), or at an appropriately registered reference laboratory. The investigator will report the UPT results on the eCRFs, in the subject's medical records, and in independent records maintained at the study site. The UPT used must have a minimum sensitivity of 25 mIU of β -hCG/mL.

13. END OF STUDY CRITERIA

At the end of each subject's participation in the study, the investigator will complete an End of Study Disposition form for all completed and discontinued subjects.

13.1 Completion of the Study

Subjects who complete the four-week course of treatment as specified in this protocol and return for Visit 9/EOS will be considered to have completed the study.

13.2 Subject Discontinuation

A subject may be withdrawn from the study prior to completion for any of the following reasons:

- AEs
- Death
- Lack of efficacy (defined as the lack of expected or desired effect related to a therapy)
- Lost to follow-up
- Non-compliance with study drug
- Physician decision
- Pregnancy
- Progressive disease (defined as a disease process that is increasing in extent or severity)
- Protocol deviation
- Study terminated by Sponsor

- Withdrawal by subject; NOTE: if the subject decides to withdraw from the study due to an AE then it should be classified as withdrawal due to an AE
- Other (e.g., any reason that may affect the outcome of the study or safety of subjects)

If a subject withdraws from the study prematurely for any reason, the site should make every effort to have the subject return to the clinic to perform all of the required visit activities for Visit 6 if the subject is withdrawing during the treatment phase of the study or Visit 9 if the subject is in the post-treatment follow-up phase of the study and to collect and reconcile all test articles (if applicable). If the subject will not return to the clinic, the site should make every attempt to contact the subject; otherwise the subject will be considered lost to follow-up.

When a subject is withdrawn from the study for a test article related AE (as defined in [Section 14.2](#)), when possible, the subject should be followed until resolution or stabilization of the AE. If the subject is discontinued from the study due to pregnancy, the pregnancy and its outcome should be followed.

Subjects who are prematurely withdrawn or discontinued from the study will be replaced until approximately 20 subjects have completed the study.

13.3 Study Termination

The study may be terminated by the investigator or the Sponsor. If, in the opinion of the investigator, clinical observations made during the study suggest that it may be unwise to continue, he or she may stop the study. A study termination by the investigator will be reported to the Sponsor.

In addition, a written statement fully documenting the reasons for this action will be submitted to the Sponsor by the investigator within five working days.

In the event that the Sponsor chooses to discontinue or terminate the study, appropriate notification will be given to the investigator.

14. ADVERSE EVENT REPORTING

14.1 Adverse Event Definitions

An **adverse event** is any untoward medical occurrence associated with the use of a drug in humans, whether or not considered drug related.

An AE (also referred to as an adverse experience) can be any unfavorable and unintended sign (e.g., an abnormal laboratory finding), symptom, or disease temporally associated with the use of a drug, without any judgment about causality. An AE can arise from any use of

the drug (e.g., off-label use, use in combination with any drug) and from any route of administration, formulation, or dose, including an overdose.

A suspected adverse reaction is any AE for which there is a reasonable possibility that the drug caused the event. "Reasonable possibility" means there is evidence to suggest a causal relationship between the drug and the AE.

An **adverse reaction** is any AE caused by a drug. Adverse reactions are a subset of all suspected adverse reactions for which there is reason to conclude that the drug caused the event. A suspected adverse reaction implies a lesser degree of certainty about causality than adverse reaction, which means any AE caused by a drug. For the purposes of prescription drug labeling, the term adverse reaction means an undesirable effect, reasonably associated with the use of a drug that may occur as part of its pharmacological action or may be unpredictable in its occurrence.

An AE or suspected adverse reaction is considered "unexpected" if it is not listed in the Investigator Brochure (IB) or is not listed at the specificity or severity that has been observed; or, if an IB is not required or available, the event is considered "unexpected" if it is not consistent with the risk information described in the general investigational plan or elsewhere in the current application. For example, under this definition, hepatic necrosis would be unexpected (by virtue of greater severity) if the IB referred only to elevated hepatic enzymes or hepatitis. Similarly, cerebral thromboembolism and cerebral vasculitis would be unexpected (by virtue of greater specificity) if the IB listed only cerebral vascular accidents. "Unexpected," as used in this definition, also refers to AEs or suspected adverse reactions that are mentioned in the IB as occurring with a class of drugs or as anticipated from the pharmacological properties of the drug, but are not specifically mentioned as occurring with the particular drug under investigation.

Timely and complete reporting of all AEs assists the Sponsor and/or their designee in identifying any untoward medical occurrence, thereby allowing:

- 1) protection of the safety of study subjects;
- 2) a greater understanding of the overall safety profile of the test article;
- 3) recognition of dose-related test article toxicity;
- 4) appropriate modification of study protocols;
- 5) improvements in study design or procedures; and
- 6) adherence to worldwide regulatory requirements.

